## 5.4.3 Extent of Disease

Number of patients with target lesions only, non-target lesions only, and both target and non-target lesions will be summarized. Individual disease sites for target or non-target lesions will be summarized.

## 5.4.4 Prior Systemic Cancer Treatment

The following will be summarized categorically unless stated as a continuous parameter.

- Type of prior anti-cancer treatment
- Number of prior anti-cancer treatment
- Time since last anti-cancer treatment prior to study enrollment will be summarized as a continuous parameter

## 5.5 Efficacy Analysis

## 5.5.1 Primary Efficacy PFS Analysis

PFS analysis will be performed using a stratified log-rank test. Stratification factors will include: prior chemotherapy use (yes, no), chemotherapy backbone (exemestane or fulvestrant), and geographic region (US, Non-US/Non-Asia, Asia). Patients with missing stratification factor will be included in the primary efficacy analysis by merging them into the largest category for that factor. Misclassification of stratification factor will be analyzed as the actual (or ITT) analysis. A sensitivity analysis using the planned (or appropriate strata) will be performed. Seri+BB will be compared relative to pla+BB using a one-sided significance level at 0.025.

## 5.5.2 PFS Sensitivity and Subgroup Analysis

PFS will be performed using a variety of methodology to assess the sensitivity to deviations and covariate factors. The same one-sided significance level at 0.025 will be used for all situations.

- Unstratified log-rank test will be performed and a Cox proportional hazards model with treatment only in the model to estimate the hazard ratio and 95% confidence intervals
- Treatment group comparison using interval-censored methods
- Evaluation of influences of baseline covariates and biomarker factors using stepwise selection methods
- Treat all censors on the seribantumab arm as events on the date of censorship
- Cox proportional hazard models will include treatment and covariate in the model. Additional models will include treatment, covariate, and the interaction effect in the model. Hazard ratios and 95% confidence intervals will be reported for all models. In addition, median event estimates and 95% confidence intervals will be reported. Forest plots of the hazard ratio estimates and confidence intervals will be displayed for the aforementioned models.

PFS will also be analyzed using IRR. PFS will be analyzed using a stratified Cox proportional hazard models similar to the primary analysis. Cox proportional hazard models will include treatment and covariate in the

model. Additional models will include treatment, covariate, and the interaction effect in the model. Hazard ratios and 95% confidence intervals will be reported for all models. In addition, median event estimates and 95% confidence intervals will be reported. Forest plots of the hazard ratio estimates and confidence intervals will be displayed with for the aforementioned models.

## 5.5.3 OS, TTP and ORR Secondary Efficacy Analysis

OS and TTP will be analyzed in the all study populations defined earlier as time-to-event analyses. Stratifed and unstratified log-rank tests will be performed for the ITT study population.

Frequencies and percentages of ORR responders will be summarized. CMH and Pearson's chi-square test will be performed for responders. A relative risk estimator will be used to contrast the treatment effects. Risk difference estimate and 95% confidence intervals will be calculated using the normal approximation.

Waterfall plots for best response and best percentage change will be displayed for study and subpopulations.

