# 10.2. Statistical Hypothesis and Determination of Sample Size

The primary hypothesis is to test for differences in progression-free survival (PFS) distributions.

A stratified log-rank test will be used to analyze PFS differences with the stratification factors in the model: Statistical significance will be determined by using a one-sided type I error of 0.10. A stratified Cox proportional hazards model will be used to estimate the hazard ratio using geographic region (US, non-US) and bone-only disease (yes, no) as stratification factors.

The median PFS for the control arm (fulvestrant + placebo) is assumed to be 4.0 months in this patient population. A total of 58 PFS events will be required across two treatment arms randomized in a 1:1 ratio giving 80% power to detect a hazard ratio (HR)  $\leq$  0.57 (mPFS: 4 v 7), assuming a 1-sided significance level of 0.10. Approximately 200 patients will need to be screened in order to accrue 80 randomized in approximately 16 months with a total study duration of 20 months.

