### 10.5.2. Secondary Efficacy Analysis

Overall Survival (OS) is defined as the time from the date of randomization to the date of death from any cause. Patients who are alive or lost to follow-up at the time of the analysis will be censored at the last known alive date. The majority of patients are expected to live at least 2 years, therefore the proportion of deaths at the time of the PFS analysis will not be sufficient for formal hypothesis testing of OS at that time.

Various sensitivity analyses will be performed on PFS and OS which will be further detailed in the SAP. PFS and OS will also be analyzed as an unstratified log-rank test for the primary and all sensitivity analysis as well. Other analyses include a PFS sensitivity analysis performed by declaring all censors as events and testing with a stratified log-rank.

Objective Response Rate (ORR) is defined as the proportion of patients with a RECIST v1.1 response recorded from randomization until disease progression characterized as either a Complete Response (CR) or Partial Response (PR) relative to the total number of evaluable patients. Frequency and percent will be as descriptive statistics while a Cochran-Mantel-Haenszel (CMH) test stratified by stratification factor will be tested. A chi-square test without stratification will also be presented. Frequency and percent along with 95% CI will be calculated

Time to Progression (TTP) is defined as the time from the date of randomization to the date of objective tumor progression. Those patients without objective tumor progression will be censored at the date of last tumor assessment documenting no objective progression. Patients who died prior to first scan will be censored on the date of death.

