## 5.3.3 Analysis of Key Binary Endpoints

Frequencies and percentages will be reported for binary endpoints. The rate of binary endpoints between 2 treatment arms will be compared using a Cochran Mantel-Haenszel (CMH) test stratified according to the stratification factors and a Pearson  $\chi^2$  test, both at a 2-sided,  $\alpha = 0.05$  level. The relative risk ratio estimate will be used to contrast treatment effects on response rates. Point estimates of the rates for each treatment arm will be provided along with the corresponding exact 2-sided 95% CI using exact methods based on the binomial distribution.

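### The normal-approximation interval for the ORR risk difference was not adapted to about 40 patients per arm, and it under-covers if one arm's response rate is very low

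*SAP*

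**What the plan says.** SAP 5.5.3 sets the between-arm ORR analysis: "CMH and Pearson's chi-square test will be performed for responders", then "A relative risk estimator will be used to contrast the treatment effects", then "Risk difference estimate and 95% confidence intervals will be calculated using the normal approximation". SAP 5.3.3 repeats the relative measure for binary endpoints ("The relative risk ratio estimate will be used to contrast treatment effects on response rates") but asks for exact intervals on each arm's own rate: "corresponding exact 2-sided 95% CI using exact methods based on the binomial distribution". No rule covers an arm with no responders.

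Protocol 10.5.2 asks for a 95% CI on ORR without naming a method, and adds a stratified CMH test and an unstratified one ("A chi-square test without stratification will also be presented"). The normal approximation therefore comes from the SAP alone.

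The two documents describe different trial sizes. Protocol 10.2: "A total of 58 PFS events will be required across two treatment arms randomized in a 1:1 ratio giving 80% power", and "Approximately 200 patients will need to be screened in order to accrue 80 randomized in approximately 16 months". SAP section 1 identifies its trial as 02-03-10, and SAP 5.1 plans 286 patients at 2:1. In both documents the ORR denominator is evaluable patients (Protocol 10.5.2, SAP 3.5). Neither gives an expected ORR, or any power or sample size for it.

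**The concern.** A normal-approximation (Wald) interval for a difference of two proportions estimates its width from the observed rates. When an arm has no responders, that arm contributes nothing to the estimated variance. The interval is then too short, and it vanishes if both arms are empty. At 286 patients this matters little. At about 40 per arm it can matter if responses are rare.

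Low rates are plausible here but not established. Protocol 4.1 admits bone-only disease, and the SAP appendix treats bone disease as non-measurable apart from qualifying soft-tissue components.

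At stake is the stated precision of the between-arm ORR contrast. The plan already uses exact methods for each arm, so the comparison between arms is the part left on a large-sample formula.

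**Working it through.** **Inputs.** Protocol 10.2: 80 patients at 1:1, so 80/2 = 40 per arm. SAP 5.1: 286 at 2:1, so about 191 v 95. ORR rates are assumed, over a range of 1% to 25%. The SAP's normal approximation is read as the usual unpooled Wald interval.

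**The plan's own figure.** The protocol's size comes from PFS, not ORR. Schoenfeld events = 4(z₀.₉₀ + z₀.₈₀)²/(ln 0.57)² = 4(1.2816 + 0.8416)²/0.316 = 57.1, rounded up to 58. This reproduces. Nothing in it fixes the precision of ORR.

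**Formulas.** With a/n and b/m responders and d = a/n − b/m:
- Wald: d ± 1.96·√[p̂₁(1−p̂₁)/n + p̂₀(1−p̂₀)/m].
- Newcombe: combines the Wilson limits of the two arms.
- Miettinen-Nurminen: all δ with (d − δ)² / {[p̃₁(1−p̃₁)/n + p̃₀(1−p̃₀)/m]·(n+m)/(n+m−1)} ≤ 3.84, where p̃ are the estimates restricted to difference δ.
- Coverage: the sum over all (a, b) of the binomial probabilities of the tables whose interval contains the true difference.

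**Coverage at 40 per arm, low unequal rates**

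| True rates | Wald | Newcombe | Miettinen-Nurminen |
|---|---|---|---|
| 5% v 15% | 93.5% | 97% | 94.2% |
| 3% v 10% | 92.0% | 97% | 94.9% |
| 2% v 10% | 91.0% | 98% | 96.8% |
| 2% v 5% | 86.3% | 99% | 97.2% |

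With 36 evaluable per arm, Wald coverage at 2% v 5% is 83.8%.

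**Coverage at 40 per arm, both rates at least 5%.** Wald gives 95.7% (5% v 5%), 94.1% (10% v 10%), 94.8% (20% v 20%), 93.9% (5% v 10%) and 94.0% (10% v 20%). At 2% v 2% it gives 99.3%, which is conservative.

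**Why 2% v 5% fails.** The true difference is 3 points. If the 5% arm has no responder, the Wald upper limit is always below 3 points: 0 if the other arm also has none, and −0.025 + 1.96·√(0.025·0.975/40) = 0.023 if it has one. With more responders in the other arm it falls further. The chance of no responder in the 5% arm is 0.95⁴⁰ = 12.9%, which is nearly all of the 13.7% non-coverage.

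**No responders in either arm.** Wald gives 0 ± 0. The Wilson upper limit for 0/40 is 3.84/(40 + 3.84) = 8.8%, so Newcombe gives ±8.8 points. Miettinen-Nurminen solves δ/(1−δ) = 3.84/39.5, giving ±8.9 points. The chance of this outcome is 0.98⁸⁰ = 20% if both rates are 2%, and 0.95⁸⁰ = 1.7% if both are 5%.

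**Relative risk.** It is undefined with no control responder: 0.95⁴⁰ = 13% at a 5% control rate, 0.97⁴⁰ = 30% at 3%.

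**At the SAP's own size.** At 191 v 95, Wald coverage is 93.8% to 95.0% over the rate pairs tried, except 90.9% at 2% v 2%. The method is mostly adequate for the trial it was written for.

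**Two sparse tables at 40 per arm (seribantumab v control)**

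| Responders | Wald | Miettinen-Nurminen | Newcombe | Pearson p | Fisher p | Barnard p |
|---|---|---|---|---|---|---|
| 4 v 0 | 0.7% to 19.3% | 0.7% to 23.2% | −0.6% to 23.1% | 0.040 | 0.116 | 0.043 |
| 6 v 1 | 0.4% to 24.6% | 0.05% to 27.1% | −0.6% to 26.7% | 0.048 | 0.108 | 0.059 |

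**The case against.** The strongest case on the other side has four parts.

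- **Coverage is close to nominal for many plausible rates.** This stands. A reader might infer that the ORR error bars are wrong throughout. The documents give no ORR, so they cannot support that. Material under-coverage needs one arm at roughly 1% to 3% and the other low but different.
- **Wald does not manufacture significance.** This also stands. A reader might infer from 4 v 0 or 6 v 1 that the plan would declare a difference that sound small-sample inference rejects. In both tables Miettinen-Nurminen excludes zero, as Wald does, while Newcombe and the conservative Fisher test do not. Barnard's exact test sides with Wald at 4 v 0 but not at 6 v 1. Valid methods differ, so these tables are not evidence of a Wald error. They do show why a single method should be fixed beforehand.
- **Pearson's test is not badly behaved here.** Its expected counts fall below 5 when there are fewer than 10 responders in total, and a reader might infer that its p-values are then invalid. By enumeration at 40 per arm its null rejection rate peaks at about 5.9% (true rate 10%) and is 0.7% at 2%. Replacing it with Fisher or exact CMH tests trades power for strict size control, so that change is optional.
- **Little rides on it.** ORR is secondary, with no stated power or decision rule, and the exact per-arm intervals would still show the uncertainty at 0 v 0. This limits the importance of the point. It does not repair the interval for the difference, which is the comparison readers will use.

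**Conclusion.** The point holds as a modest correction to one interval on a secondary endpoint. The SAP's method suits its 286 patients and was carried over to an 80-patient protocol without adaptation.

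Three defects remain: coverage of 86% to 92% at the low, unequal rates shown; a zero-width interval when neither arm responds; and a relative risk that may not exist, with no rule for that case. The first depends on assumed rates, since the documents state none, and on 40 evaluable per arm; at 2% v 5% it worsens with 36. The zero-width interval and the undefined ratio follow from the formulas, and only their probability depends on the rates. The primary PFS analysis is untouched.

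**What to change.** In SAP 5.5.3 and 5.3.3:
- Replace the normal approximation with one named score interval for the risk difference, for example Miettinen-Nurminen. Name only one: the two common score-type intervals disagree about zero at 4 v 0 and 6 v 1, so leaving both open would allow a choice after the data are seen.
- Make the risk difference the main between-arm contrast.
- Report the relative risk only when both arms have responders, and say what is shown otherwise.

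Fisher or exact CMH tests may be added but are not needed to cure this point.

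The cost is one or two sentences and standard software. The downside is slightly wider intervals in sparse data: at 4 v 0 the upper limit moves from 19.3% to 23.2%. The change belongs in a SAP written for this protocol's 80 patients, and should be settled before database lock, by when Protocol section 10 requires the SAP to be complete.

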## 5.5.4 Exploratory Biomarker Analysis

Descriptive statistics will be used to characterize the biomarkers within treatment groups over time. Continuous markers will be summarized using the change from baseline and observed values. Change from baseline to last observed will be analyzed using an ANCOVA model with baseline and stratification factors, treatment as fixed effects. Interaction effects may be tested and included in the final model(s) if deemed important. Least squares means and 95% confidence intervals will be reported. Categorical markers will be summarized using shift from baseline to last observed. CMH test using stratification factors will be used to analyze parameters.

The biomarker relationship to outcomes OS and PFS will be analyzed using a stratified log-rank test. Screening values of biomarker values will be used in the following analysis. Continuous biomarker values will be dichotomized by  $\geq$  median, < median; as well as quartiles. Biomarker analyses will consist of performing analysis on the overall PFS endpoint. Kaplan-Meier displays will be reported. Kaplan-Meier curves will include the following:

- seribantumab, Control According to categorical grouping
- Control Only According to categorical grouping

Included in the graphs will be hazard ratio and 95% confidence intervals, median PFS and 95% confidence intervals, number and percentage of events and censors. These will be performed for all markers identified. Forest plots will be used to describe the biomarker subgroups relationship via hazard ratios and 95% confidence intervals.

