### Arm B (Comparator Arm):

- Placebo: intravenously (IV) on days 1 and 15 of each 28-day cycle
- Fulvestrant: 500 mg IM on days 1 and 15 of Cycle 1, and on day 1 of each subsequent 28 day cycle

Treatment must start within 7 days following randomization. It is intended that patients will be treated until investigator-assessed disease progression or unacceptable toxicity, whichever comes first. Tumor assessments will be measured and recorded by the local radiologist every 8 weeks (+/- 5 days) from randomization using the RECIST guidelines (version 1.1). Tumor assessments will be performed every 8 weeks regardless of dose delays or dose interruptions, until investigator-assessed progressive disease. Patients who come off study treatment prior to disease progression, for reasons including patient or physician decision or unacceptable toxicity, will continue to undergo tumor assessments every 8 weeks (±5 days) until investigator assessed PD. Patients will be treated according to local assessment of tumor scans, and the primary analysis will be conducted based on investigator assessments.

All patients will have a follow-up visit scheduled 30 days (±7 days) after the last dose of study treatment, regardless of reason for treatment termination. Patients will not be allowed to cross over from placebo to seribantumab.

Survival follow up will be required for all patients every 2 months from the 30-day follow-up visit until death, loss to follow-up, withdrawal of consent, or study termination. After patients discontinue study treatment, subsequent anti-cancer therapies will be collected at the same time as survival follow-up.

An independent data monitoring committee (DMC) will be established to monitor emerging safety data and evaluate for trial efficacy. The DMC will regularly monitor safety data over the course of the study in accordance with the DMC Charter.

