-  Seribantumab PK: all patients; in relation to seribantumab infusion
  - a C1W1: immediately after the end of the Seribantumab infusion (+15 mins)
  - b C1W3, C2W1, C2W3: pre-dose
-  Immunogenicity samples should be collected for all patients prior to dosing.
-  In the event a patient experiences an infusion reaction at any point in the study, an anti-Seribantumab antibody assay will be taken within 24 hours of the event, in addition to the scheduled time-points. For patients who experience a Grade 3 or 4 infusion reaction to Seribantumab, an anti-Seribantumab antibody titer will be taken as close to the onset of the infusion reaction as possible, at the resolution of the event and 28 days (+/- 2 days) following the event.
-  Disease evaluation per RECIST version 1.1.
-  Tumor sample is to be collected for all HRG positive patients that receive HRG results for eligibility based on testing of archived samples. An additional sample is not required for patients who underwent a fresh biopsy for eligibility testing.
-  Fulvestrant PK: all patients: prior to seribantumab injection
-  Serum for biomarkers should be collected pre-infusion on week 1 of each cycle for all patients
-  End of treatment (30-day Follow-up) visit should be completed within 30 days of the last dose of study drug
-  Should patients refuse or drop out of survival follow-up, attempts should be made to obtain any death information available via public records.
-  One reading prior to infusion with seribantumab.
-  AE/SAE collection to be included. S/AE assessment and reporting will proceed as outlined in Sections 9.2 and 9.3
-  All patient hospitalizations and/or hospital visits should be collected, whether or not associated with an adverse event.
-  In addition to the timepoints noted, MUGA or Echocardiogram should be performed post-screening for any study patient who develops symptoms consistent with new onset of congestive heart failure.
-  Unless performed within the last 4 weeks as part of assessments in the previous cycle
-  Sample to be collected prior to any study treatment.

Proprietary and Confidential Page 44 of 65

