#### 7.7. Disease Evaluation

Tumor response will be evaluated by the local radiologist according to the Response Evaluation Criteria in Solid Tumors (RECIST) version 1.1 (Eisenhauer et al., 2009) to establish disease progression by CT or MRI. In addition, other radiographic or scintigraphic procedures (such as radionuclide bone scans), as deemed appropriate by the investigator, will be performed to assess sites of neoplastic involvement. The same method of assessment must be used throughout the study. Please refer to image acquisition guidelines for the requirements for image collection and scanner qualification. Investigators should choose target and non-target lesions in accordance with RECIST v1.1 guidelines. Follow-up measurements and overall response should also be in accordance with these guidelines. To be assigned a status of confirmed partial response (PR) or complete response (CR), changes in tumor measurements must be confirmed by repeated assessments that should be performed ≥30 days after the criteria for response are first met.

Disease should be assessed every 8 weeks (±5 days) from randomization regardless of treatment schedule until investigator-assessed progression. In cases where there is a suspicion of disease progression prior to the next scheduled scan, an unscheduled assessment should take place. All patients who come off study treatment prior to disease progression for reasons including patient or physician decision or unacceptable toxicity will continue to undergo tumor assessments every 8 weeks (±5 days) until investigator-assessed progression of disease.

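### The exploratory serum-marker comparison uses each patient's last on-treatment sample, which falls about two cycles later in the seribantumab arm if PFS is 4 v 7 months, so a marker that keeps drifting would show a false difference between arms

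*SAP*

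**What the plan says.** SAP 5.5.4 sets the test for continuous markers: "Change from baseline to last observed will be analyzed using an ANCOVA model with baseline and stratification factors, treatment as fixed effects". Categorical markers use the same endpoint ("Categorical markers will be summarized using shift from baseline to last observed") with a CMH test. SAP 5.3.4 puts such models at two-sided 0.05.

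Marker behaviour over time is handled only descriptively: "Descriptive statistics will be used to characterize the biomarkers within treatment groups over time". The one optional addition to the model is "Interaction effects may be tested and included in the final model(s) if deemed important". No visit term, common time point or repeated-measures model is named for markers.

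The sampling rule is in the protocol, Section 6.1: "Serum for biomarkers should be collected pre-infusion on week 1 of each cycle for all patients". The schedule table marks no biomarker serum at the 30-day follow-up. Section 3.1 sets when treatment, and therefore sampling, ends: "It is intended that patients will be treated until investigator-assessed disease progression or unacceptable toxicity, whichever comes first". Section 7.7 sets the scan interval: "Disease should be assessed every 8 weeks (±5 days) from randomization regardless of treatment schedule until investigator-assessed progression". Section 10.2 gives the planning assumption: "The median PFS for the control arm (fulvestrant + placebo) is assumed to be 4.0 months in this patient population", against 7 months with seribantumab.

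**The concern.** The last sample is taken when treatment is about to end or when data are cut, at a different cycle for each patient. If seribantumab prolongs PFS, its patients are sampled later. Baseline adjustment does not correct this, because the difference in sampling time arises after randomization.

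Two errors could follow. A marker that moves steadily with time on fulvestrant, and not at all with seribantumab, would show a treatment difference. And because many last samples sit close to progression, a real early effect of the drug could be blurred by changes due to the disease. Protocol 8.7.3 collects this serum partly to find markers that help evaluate response to seribantumab, so a false on-treatment signal could be read as pharmacodynamic evidence.

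**Working it through.** **Inputs from the protocol.** Median PFS 4 v 7 months (HR 0.57), 80 patients at 1:1, 16 months accrual, 20 months total (10.2); scans every 8 weeks (7.7); serum every 28 days on treatment (6.1). **Input from the SAP.** Two-sided 0.05 (5.3.4).

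**Assumptions, because the documents give none.** Exponential PFS, uniform accrual, marker SD 1, baseline correlation 0.5, the same drift in both arms, no effect of seribantumab on the marker, no link between marker and progression, no early stopping for toxicity. The stratification factors were left out of the model.

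**Step 1: the plan's own figure.** The documents state no number for the marker analysis. The PFS assumption behind it reproduces:

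events = 4 × (1.2816 + 0.8416)² / (ln 0.57)² = 4 × 4.508 / 0.3160 = 57.1, rounded up to 58, as stated in protocol 10.2.

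**Step 2: when the last sample falls.** Let T be the earlier of the scan that detects progression (PFS time rounded up to a multiple of 56 days) and the data cut. The last sample is number k = ceil(T/28) − 1 after baseline.

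| | Control | Seribantumab | Difference |
|---|---|---|---|
| Mean at the 20-month cut | week 20.7 (5.2 cycles) | week 28.5 (7.1 cycles) | 7.9 weeks (before rounding) |
| Median at the 20-month cut | week 20 | week 24 | 4 weeks |
| Mean with complete follow-up | week 25.4 | week 44.0 | 18.7 weeks (before rounding) |

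The mean gap at the cut is 7.9 / 4 = 1.97 cycles.

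**Step 3: expected false effect.** For linear drift of d SD per cycle it is d × 1.97. For example, 0.1 × 1.97 = 0.20 SD and 0.2 × 1.97 = 0.39 SD.

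**Step 4: the ANCOVA by simulation.** 40 per arm, change regressed on baseline and treatment, 4,000 trials per row.

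| Drift (SD per cycle) | False effect (SD) | Rejection |
|---|---|---|
| 0 | 0.00 | 5.1% |
| 0.05 | 0.10 | 8.2% |
| 0.1 | 0.19 | 13.5% |
| 0.2 | 0.39 | 28.3% (27% in a repeat) |
| 0.3 | 0.59 | 35.0% |

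**Step 5: when the problem disappears.** With a 4-month median in both arms, drifts of 0.1 and 0.2 give 5.5% and 4.6% rejection. With drift that levels off within the first cycles, the false effect is 0.01 to 0.05 SD and rejection is about 4% to 6%.

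**Step 6: which fixed visit.** The proportion progressed by day t is 1 − 2^(−t / (30.4375 × median)).

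| Visit | Day | Control | Seribantumab |
|---|---|---|---|
| C2W1 | 28 | 15% | 9% |
| C3W1 | 56 | 27% | 17% |
| C4W1 | 84 | 38% | 24% |

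A complete-case ANCOVA at C3W1 held 4.2% to 5.6% rejection in the simulation, but only because marker and progression were simulated as unrelated. In practice it would compare survivors selected differently in the two arms.

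**The case against.** A reader might infer that any time trend in a marker will be reported as a seribantumab effect. The documents do not support that. The bias needs a PFS difference and also a marker that is still moving between the two arms' last-sample times. Step 5 shows that it vanishes without either. Linear drift without limit is the unfavourable case: at 0.2 SD per cycle it implies a mean shift of about 0.2 × 7.1 = 1.4 SD by the last sample.

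A reader might also infer that the search for predictive markers is compromised. It is not. The next paragraph of SAP 5.5.4 relates markers to PFS and OS using screening values, and last-observed values do not enter.

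The stakes are low. Change in serum markers is not a listed objective, SAP 3.9 details only HRG status and calls further analyses exploratory, and no decision rule depends on this test. That stands, and it limits the weight of the point.

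The by-time summaries, and the cycles-started table in SAP 5.6.1, would let a careful reader see drift and unequal exposure. They do not repair the p-value or the least-squares means.

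Finally, the SAP describes another design (protocol 02-03-10: fulvestrant or exemestane, 2:1, 195 events), and its Section 3.9 mentions only baseline samples. The sizes above are for the protocol's 80 patients and were not computed for 286. The mechanism should carry over, since the SAP also assumes 4 v 7 months and 5.5.4 analyses change over time, but the numbers should not be transferred.

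**Conclusion.** The point holds as a limited one. The tested contrast compares arms at sampling times that the primary outcome sets. Under the plan's PFS assumption the mean gap is about two cycles at the 20-month cut. Across assumed linear drifts of 0 to 0.2 SD per cycle, false rejection runs from the nominal 5% to about 27%. Whether any marker drifts in this way is unknown. The categorical shift and CMH analysis shares the mechanism but was not simulated. The primary PFS test and the analyses of screening markers against PFS and OS are untouched. The point is worth correcting because the cost is small and the SAP already uses a suitable model elsewhere: Section 5.6.5 analyses QTcF with time, treatment and their interaction.

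**What to change.** In SAP 5.5.4, replace last observed as the tested endpoint by one of the following, chosen in advance:

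- change from baseline at C2W1 pre-infusion, with the same ANCOVA; or
- one repeated-measures mixed model over cycles 2 to 4 with baseline, stratification factors, treatment, visit and treatment-by-visit, including every patient with any post-baseline sample, and with the visit contrast to be tested named.

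Use C2W1 for the categorical shift and the CMH test. Keep last observed as a descriptive summary. Do not make a complete-case test at C3W1 the main contrast, given the 27% v 17% progressed by day 56.

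The cost is SAP wording and programming, since the samples are already scheduled. Patients who stop before C2W1 have no post-baseline value in the current analysis either. The price is that late samples leave the test and C2W1 shows only early effects. Some outcome-related dropout remains by cycles 3 and 4, which the mixed model handles only if data are missing at random.
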